Protocol description	Written consent will be obtained after complete information of the subjects about the objectives, and the nature and possible risks of the study (informed consent form in duplicate, one copy given to the volunteer). The protocol will be explained in details, with objectives and constraints, according to the information form, by the scientist in charge. A clinical exam and a check-up of all selection criteria will be performed by the main investigator or another medical doctor.  At the inclusion visit, subjects will have a medical exam including questionnaire

	
regarding past medical history, family background, medical treatments and standard clinical exam (weight, height, blood pressure) and a blood sampling. A food frequency questionnaire will also be completed. The conformity to the selection criteria will be checked during this medical exam. The selected subjects will be definitely included after validation of the selection criteria by the investigator.
 
The volunteers will consume in 3 distinct experimental periods either a control drink (oral nutritional complement Fresubin, 250 mL), or 240g banana (and 150 ml Fresubin), or 300g tomato (with 12 g sunflower oil and 150 mL Fresubin). Every volunteer will consume the 3 test foods, in a randomized order. After test food intake, urine will be collected over 24h in 7 fractions. Blood samplings will be performed before the food consumption (t0) and in post-prandial period (4 samplings at 1h, 2h, 4h et 6h), as well as on the following day in fasting state (t24h). the volunteers will follow a tomato and banana-free diet during the study days, as well as a more restrictive diet, without plant-based food, on the sampling days and on the day before. A 24h recall will be filled for the dietary intakes on the day before the sampling days (D2).
 
Samples will be analyzed using an untargeted metabolomics approach (LC-MS, GC-MS et RMN) with the aim to identify new biomarkers of tomato and banana intake.
 
The total volume of sampled blood will be 154 ml per subject.

Duration	
Duration of the study for every volunteer : 8 weeks
 
Total duration of the study: 6 months for the subject selection and realization of all experimental periods for all the volunteers
 
Total duration of the project : 3 years

Indemnities	350€ per subject

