### **4 – PROTOCOL DESCRIPTION**

The present project is a randomized, controlled, crossover study with 12 subjects. A cross-over design has been selected as each subject can serve as his/her own control thereby minimizing variations. Limitations attributed to cross-over designs are possible order or carry-over effects. These effects will however be minimized due to a randomized intervention order. The study design does not allow blinding as intervention is the ingestion of different foods.

In this study, we will assess the metabolomic profiles of human biofluids after consumption of two different foods: banana (240g peeled fruit) and tomato (300g fresh fruit) in order to identify novel biomarkers for each food. As a control diet, a high energy high protein drink, Fresubin ® 2kcal fiber (Fresinius kabi) will be used. As shown in the general study plan, the intervention comprises three dietary intervention periods of 4 days each for each food of interest and the control drink. Each

intervention period will be separated by a washout period of minimum 3 days (and maximum 10 days). Volunteers will be randomly assigned to a different food at each time point. Volunteers will be asked to maintain their normal physical activity and follow the dietary recommendations between intervention periods; they will receive an information form containing the description and objectives of the project, and detailed instructions. A volunteer’s booklet will also include simple information about nutritional metabolomics and a calendar marked with their visits to our facilities.

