The volunteers recruited for this project will be asked to eat three different foods, banana, tomatoes and a control drink (Fresubin ® 2kcal fiber) in order to identify novel biomarkers for each test food. Subjects will be randomly assigned to each test food at different time points of the study. As shown in the general study plan, there will be three dietary interventions:

- **Intervention 1:** Volunteers will consume the **control beverage Fresubin ® 2kcal fiber (250 mL)**.

- **Intervention 2:** Volunteers will consume **240g of peeled banana plus Fresubin ® 2kcal fiber (150 mL)**.
- **Intervention 3:** Volunteers will consume **300g of raw tomato with sunflower oil (12g) and Fresubin ® 2kcal fiber (150 mL)**.

Fresubin is a beverage composed mainly of milk protein, vegetable oils (rapeseed oil, sunflower oil) carbohydrates, vitamins minerals and trace elements (Detailed composition in Appendix 3). For the purpose of this study volunteers will drink the neutral flavored beverage.

Each intervention period will be separated by a washout period of at least 3 days (maximum 10 days). Volunteers will be asked to maintain their normal physical activity and diet between intervention periods; they will receive an information form containing the description and objectives of the project. Volunteers will be randomly assigned to a different food at each intervention period.

Following the study design shown in the general study diagram, the **run-in phase (Day1 and Day2)** participants will follow a restricted diet (described in Appendix 4) and will avoid the intake of banana or tomato in any form. On **Day 2** volunteers will also avoid the intake of banana and tomato in any form and will exclude phytochemical-rich foods such as tea, coffee, wine and other plant foods to avoid noise in the metabolomic profile (recommendations described in Appendix 5). For dinner in this day, volunteers will prepare a standardized dinner which composition will be given by the investigators (rice and chicken meal, composition in Appendix 6). After dinner subjects will begin the overnight fasting period. All foods consumed on day 2 will be reported in the 24-hour recall questionnaire applied by a nutritionist the day of the dietary intervention.

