In the morning of Day 3, subjects will arrive fasted at Investigational Site at around 7.30 am. As stated previously volunteers will be assigned randomly to one of the three interventions, Fresubin ® 2kcal fiber, 240g of banana plus control drink, or 300g of tomato plus control drink. Throughout the intervention, subjects will have free access to water, maximum 250ml of water per hour until 6 hours after intervention (1.5L in total).

A trained phlebotomist will place a catheter on the subject's arm before the intake of the test foods to collect the baseline sample. Then four other samples will be collected postprandially after **1h, 2h, 4h, and 6h**.

A total of **7 urine samples** will be collected. The first void of urine will be collected by the subjects at home upon the morning of Day 3 and the rest of the samples after the intake of the test foods as follows: **0-1h, 1h-2h, 2h-4h, 4h-6h**. The urine samples corresponding to **6h-12h** and **12-24h** interval will be collected by volunteers at home until the morning of **Day 4**. Urine samples will be kept at 4°C between collections; the use of preservatives will not be needed.

After the 6h collection of blood, the peripheral catheter will be removed and subjects will have lunch composed of rice and chicken meal, then subjects will be allowed to go home. Before leaving the Investigation center, participants will be instructed to prepare a standardized dinner based on chicken and rice. Volunteers will not be allowed to eat or drink anything except water and the standardized dinner.

On the morning of **Day 4**, subjects will arrive fasted at the investigation center at around 7.30 am in order to collect the **24h** blood sample and will deliver the **6h-12h** and **12-24h** urine collection. Afterwards participants will receive a breakfast (free composition) on site and be allowed to follow their normal diet until the run in phase of the following intervention period initiates. This procedure will be repeated for each intervention (1,2,3) separated by a minimum 3 day period (=7 days between visits).

*Table 1. Summary of trial procedures*

	Who	Where
Day 1: Run in		
Restricted diet: no banana or tomato intake	Volunteer	At home
Day 2: Run in		
Restricted diet: no intake of tomato, banana, tea, coffee, wine, fruit juices, plant foods. Dinner based on chicken and rice,	Volunteer	At home

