## **Appendix 5 : Restricted diet for Day 2**

No intake of tomato in any form : raw tomato or cooked tomato, tomato products (sauce, paste, ketchup) and dishes containing tomato (pizza, soup, ratatouille, chili con carne...).

No intake of banana in any form.

No intake of plant-based beverages : coffee, tea, herbal teas, chocolate, fruit juices, wine, beer.

No intake of fruits and vegetables, legumes, salad, breakfast cereals, wholegrain products.

No intake of soft drinks.

No alcohol

Animal products (meat, fish, eggs, etc...), dairy products (butter, cream, yogurt, cheese), pasta, white rice, potatoes, white bread are allowed.

Water and milk are the only beverages allowed.

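### The protocol gives conflicting diet instructions for the washout and for Day 2, does not say which governs, and leaves washout and Day 1 intake unrecorded

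*Protocol*

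**What the plan says.** **Between periods.** Section 4 asks volunteers to "follow the dietary recommendations between intervention periods" and does not define them. Section 6-1 asks them to "maintain their normal physical activity and diet between intervention periods" and later says that, once the Day 4 breakfast is over, they will "be allowed to follow their normal diet until the run in phase of the following intervention period initiates". Table 2 (section 6-2) marks the restricted diet on Days 1 to 3 of each period and on no other day. The Summary bans tomato and banana on the study days, a term that is not defined anywhere.

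**Day 2.** The Summary describes "a more restrictive diet, without plant-based food, on the sampling days and on the day before". Section 6-1 excludes phytochemical-rich items and other plant foods, and refers to Appendix 5 for the detail. Table 1 has "Restricted diet: no intake of tomato, banana, tea, coffee, wine, fruit juices, plant foods", and the same entry prescribes a dinner of chicken and rice. Appendix 5 states that "pasta, white rice, potatoes, white bread are allowed". Appendix 6 builds the Day 2 and Day 3 dinner from chicken, white rice and white bread, in unlimited amounts.

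**Recording and analysis.** A nutritionist applies a 24-hour recall on Day 3, covering Day 2, to check compliance (sections 6-1 and 7-2-2). The SAP's plasma analysis screens ions against the 00h sample. Its urine analysis compares banana with control and tomato with control, and mentions no pre-dose sample, although a first-void urine is collected in every period (sections 6-1 and 6-3-2).

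**The concern.** The study looks for food-specific signals in a small crossover: 12 volunteers, with the aim that 10 complete. The diet rules are there to keep background signal low. If staff cannot tell whether the test foods are allowed in the washout, some volunteers may eat them and others not. A control period could then start with some banana or tomato signal already present. Nothing records intake in the washout or on Day 1, so such periods could not be identified afterwards.

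On Day 2, a volunteer who eats potatoes complies with Appendix 5 and departs from the wording of the Summary and Table 1. This matters to the volunteer as well as to the data. A significant protocol deviation is a ground for withdrawal (section 5-4), and a volunteer excluded as obviously non-compliant receives no compensation (section 5-6).

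**Working it through.** **1. The plan's own calendar.** From one Day 3 to the next: Day 4 (1) + washout (3) + run-in (2) + 1 = 7 days, as section 6-1 states. Participation: 3×2 + 3×1 + 3×1 + 2×3 = 18 days, as section 6-4 states. With 10-day washouts it is 12 + 20 = 32 days, or 4.6 weeks, in line with that section's limit of 5 weeks.

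**2. Time without the test foods before each later Day 3.**
- Normal-diet wording: only the two run-in days are guaranteed. Counting from midnight before Day 1 (an assumption) to 7:30 on Day 3 gives 48 + 7.5 = 55.5 h. Test foods could be eaten on Day 4 after the 24 h sample and throughout the washout, which is 1 + 3 = 4 to 1 + 10 = 11 days per interval.
- If the recommendations in section 4 did exclude the test foods throughout (no passage says so): 1 + 3 + 2 = 6 to 1 + 10 + 2 = 13 full days. The last possible intake would be the earlier test dose, at least 7 × 24 = 168 h before.
- Period 1 has only the two-day run-in on either reading, so the conflict concerns periods 2 and 3.

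**3. What could remain, as an assumed worst case.** The documents give no half-lives. Take a volunteer who eats a dose-sized amount at the last permitted moment, with residual = 2^(−t / half-life).

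| Assumed half-life | t = 55.5 h | t = 168 h |
|---|---|---|
| 12 h | 4% | <0.1% |
| 24 h | 20% | 0.8% |
| 48 h | 45% | 9% |

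**4. Effect on the contrast.** Assume a food response of 1.0, other background of 0.1, and the same residual r in the food and the control period.
- Raw difference: (1.1 + r) − (0.1 + r) = 1.0, unchanged.
- Ratio: (1.1 + r) / (0.1 + r). With r = 0 it is 11. With r = 0.20 it is 1.30 / 0.30 = 4.3, and the log contrast falls from ln 11 = 2.40 to ln 4.33 = 1.47, about 39% smaller.
- By the same formula, r = 0.04 gives about 13% and r = 0.45 about 57%.

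The SAP log-transforms the data for the urine OSC filter, so the log scale is relevant there. It does not state the scale of the urine t test.

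**5. Baseline in urine.** The SAP's banana-and-control urine set has n = 24 = 12 × 2, one sample per volunteer and treatment. That count leaves no place for a pre-dose sample, and the text mentions none.

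**6. Day 2 wording.** The exclusion of plant foods cannot be met literally, because the Table 1 entry that contains it also requires rice, and Appendix 6 adds white bread. Appendix 5 is the only itemised list, and section 6-1 refers to it. No passage says that it overrides the Summary or Table 1.

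**The case against.** The other side has a good case on several points.

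- **Day 2 compliance.** A reader might infer that it cannot be judged. The documents do not support that. Section 6-1 points to Appendix 5, which lists allowed and forbidden foods, and the recall records everything eaten on Day 2. The broader wording in the Summary and Table 1 reads as shorthand. What stands is that no passage says which wording governs.
- **Between periods.** Both statements in section 6-1 and Table 2 agree on a normal diet. Section 4 is the outlier, and it does not say that the test foods are barred. What stands is that its recommendations and the Summary's study days are undefined, so the intended rule is open.
- **Hidden markers or biased comparisons.** A reader might infer either from washout eating. Both foods are barred on Days 1 and 2 in every version, the endpoint is acute intake followed over 24 h, and washout eating is not tied to the randomised food. An additive residual common to both arms leaves the expected raw difference unchanged. Even with r = 0.45 and no other background, the food-to-control ratio is 1.45 / 0.45 = 3.2, which is dilution and not disappearance. What stands is added variability and a smaller log-scale contrast.
- **Baseline.** Plasma is already screened against 00h. The gap is in urine only.

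**Conclusion.** The point holds as an inconsistency with a limited statistical consequence. The between-period instructions conflict, the Day 2 wording conflicts with its own appendices, and intake on Day 1 and in the washout is not recorded.

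Only compounds that persist beyond about two days are exposed, and only in periods 2 and 3 does the choice of reading matter. The true size cannot be computed from the documents. The 4% to 45% residuals rest on assumed half-lives of 12 to 48 h, a midnight start of the run-in, and a dose-sized intake at the last permitted moment. The log-contrast losses of about 13% to 57% also assume a background of 0.1 and equal residuals in both periods. They are an upper illustration, not an estimate. The likely effect is extra variability and some attenuation on the log scale in urine. It is worth correcting because the correction costs so little.

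**What to change.** 1. Reconcile the Summary, section 4, section 6-1 and Table 2 into one between-period instruction, and define the term study days. Reconcile the Summary, section 6-1, Table 1, Appendix 5 and Appendix 6 on one Day 2 list. Which dietary rule to keep is for the investigators; this review does not choose.
2. Add the date of last banana and last tomato intake to the existing Day 3 recall in all three periods. This covers the washout and Day 1, and helps whichever rule is kept.
3. In the SAP, use each period's pre-dose first-void urine as baseline in the urine comparisons, as is already done with 00h in plasma. The first void is not a timed fraction, so normalising it by volume as for the later fractions may not make it comparable; the SAP should say how it is scaled.
4. Flag periods that break the reconciled rule and repeat the food-versus-control comparisons without them as a sensitivity analysis.

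The cost is edits to wording, one recall question, and a little more analysis work.

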**6-2 SCHEME OF STUDY AND FLOW CHART**

*Table 2: Measurement calendar*

Visit													
Day of visit	Screening visit	Day 1 Run in	Day 2 Run in	Day3 Acute intervention	Day 4	Day 1 Run in	Day 2 Run in	Day3 Acute intervention	Day 4	Day 1 Run in	Day 2 Run in	Day3 Acute intervention	Day 4
Signature of subject information form and consent form	X												
Checking of eligibility criteria	X												
Clinical examination	X												
Biological test	X												
Restricted diet		X	X	X		X	X	X		X	X	X	
Biological collection													
Blood				X	X			X	X			X	X
Urine				X	X			X	X			X	X
Body assessment													
Height, weight, waist, hip circumference, body mass index.	X												
Dietary assessment													
24-hour recall questionnaire				X				X				X	
Food frequency questionnaire	X												
		Test Food A				Test Food B				Test Food C			

### 6-3 BIOLOGICAL SAMPLES

#### 6-3-1 Blood samples

We will collect 6 blood samples (8 ml), one at baseline and 5 others after the acute intervention (t= 0hr, 1hr, 2hr, 4hr, 6hr, 24hr) at each of the 3 experimental interventions (Banana, Tomato, Control drink Fresubin). These samples will be collect at the Unité d'Exploration Nutritionnelle and will be stored at the Human Nutrition Unit, INRA Centre of Theix. Volunteers will arrive at the Investigation Center in an 8-12 hour fasting state and after two days of a restricted diet. All blood samples will be processed immediately after they are drawn allowing clotting at room temperature for 30 minutes. After clotting serum will be collected in aliquots and then stored at -80°C until analysis. The whole volume of blood collected during the experimental periods is 8mL x 6 time points x3 experimental periods = 144 mL. In addition, 10 mL blood will have been collected at the screening visit. The sample collected at the screening visit will be analysis the same day of the collect by the Biochemistry Unit of Clermont Ferrand Hospital.

In total, the volume of blood collected for the whole BioBanaTom study is 154 mL.

#### 6-3-2 Urine sampling

Participants will be instructed on collecting urine according a standardized protocol and they will be provided with containers. Subjects will be asked to collect all urine samples in marked containers at the following schedule: first void of urine before intervention, 0-1h, 1-2h, 2-4h, 4-6 h, 6-12h and 12-24h (Day 4). Urine samples will be kept at 4°C until processing.

After complete collection, urine samples volumes will be recorded, urine will be centrifuged at 1800xg for 10 minutes at 4°C and separated in aliquots and stored at -80°C at the Unité de Nutrition Humaine, INRA Centre of Theix. until analysis.

Table 3: Analyses performed

ANALYSES	
Partner	Measurements
UNH, INRA Theix, France	Serum LC-MS metabolomics Urine LC-MS metabolomics
Max Rubner-Institut (MRI) Karlsruhe, Germany	Serum GC-MS and NMR metabolomics Urine GC-MS and NMR metabolomics

### 6-4 DURATION OF SUBJECT PARTICIPATION AND DURATION OF ALL TRIAL PERIODS AND FOLLOW UP IF ANY

The duration of the subject's participation is of 18 days distributed as follows:

- 3x run-in phase of 2 days (Day1 and Day2) = 6 days
- 3x intervention periods (Day3) = 3 days
- 3x collection of 24 h blood samples (Day 4) = 3 days
- 2x 3 days washout periods between interventions= 6 days

The duration of the study may be extended to 5 weeks if the wash-out periods are extended (up to 10 days).

The participation of the subjects enters within the framework of articles L1121-1 and following ones of the Public health code.

## 7 – TRIAL DESIGN

### 7-1 STUDY PARAMETERS/ENDPOINTS

#### *7-1-1 Primary study parameter*

The primary parameter in this study is the assessment of metabolites present in blood serum and urine before the dietary intervention (t=0h) and post-prandially at different time points over 24h. Metabolites will be analyzed using a non-targeted metabolomics approach (GC-MS, LC-MS and NMR). The endpoint is the identification of biomarkers of acute intake of the foods of interest through the comparison of metabolomes after either single dose of tomato, banana or control drink.

#### *7-1-2 Secondary study parameter*

A secondary endpoint is to obtain pools of urine and serum samples collected after acute intake of tomato or banana that can be shared with the international scientific community through the FoodComEx library, to be used as analytical standard or for the identification of specific metabolites of banana or tomato components.

Other secondary parameters in this study are the possible variations in endogenous metabolites detected by the metabolomics profiles that may reflect a metabolic effect of acute consumption of the tested foods. The secondary endpoint is the identification of new hypotheses on possible metabolic effects of banana or tomato that may be investigated further in others studies.

### 7-2 DESCRIPTION OF THE RESEARCH METHODOLOGY

#### *7-2-1 Anthropometry*

In order to minimize variation, all anthropometric measurements will be taken by the same person at the screening visit. These measurements will be conducted on the subject while they are wearing light, indoor clothing and while they are still fasting. Shoes and belts will be removed and pockets emptied.

#### ***Height measurement***

The subject is placed standing at a stadiometer while wearing socks or bare feet. Hats, hair slides or highly placed hair-dos must be removed or undone. The subject is asked to stand with their back to the stadiometer's backboard ensuring their feet, buttocks and occiput (back of skull) touch the board. The measuring arm is brought down to touch the top of the subject's head, pushing hair down if necessary. This is done in duplicate, obtaining measurements to the nearest 0.1cm which will be averaged.

#### ***Weighting method***

The scale is turned on (if previously off) and allowed to equilibrate. The subject removes their socks and stands on the scale. They are instructed to hold still for about 5 seconds until the scale has obtained its reading. Body weight is taken to the nearest 0.1kg. Antibacterial cleansing wipes are to be used on the scales in between uses.

#### ***Method for measuring waist circumference***

For both measurements a non-stretch tape should be used. The subject should be standing with the abdomen relaxed, arms at the sides, feet together and breathing normally. If agreed by the subject, the measurement will be made directly on the skin. It should not be taken over heavy clothing.

The tape is placed around the waist, which is defined as the mid-point between the lowest rib and the supra-iliac crest. The measurement should be taken at the end of a normal expiration ensuring the tape is not compressing the skin. If the waist cannot be easily found, the investigator should ask the subject to bend over to the side - the fold is where the waist is. The measurement is read while standing at the subject's left side and it should be recorded to the nearest 0.1cm. This should be done in duplicate.

